6.12. Possible drug interactions

No formal clinical drug interaction studies have been performed with radium-223. Any medications deemed necessary to ensure patient safety and well-being may be administered at the discretion of the investigator with the exceptions indicated in section 3.4.

7. SAFETY DEFINITIONS AND REPORTING REQUIREMENTS

Safety assessments will consist of monitoring and recording AEs, adverse events of special interest (AESI), and SAES as defined in the protocol; measurement of blood count and chemistry values specified in the protocol; and the measurement of vital signs and other tests defined in the protocol which are deemed important to the safety assessment of the study drug(s).

The Sponsor or its designee is responsible for reporting SAEs to the competent authorities, other applicable regulatory authorities, and participating investigators, in accordance with International Conference on Harmonization (ICH) guidelines, European Clinical Trials Regulation (Regulation (EU) No. 536/2014), and/or local regulatory requirements.

The Sponsor or designee is responsible for reporting unexpected fatal or potentially life-threatening events related to the use of the study drug to the Health Authorities and relevant authorities, by fax within seven calendar days of learning of its occurrence. The Sponsor or designee will report any other significant expeditable SAEs related to the use of the study medication to the corresponding competent authorities (in accordance with local guidelines), in the form of a written safety report within 15 calendar days.

7.1. Definitions of AEs

An AE is defined as an incident that is harmful to the health of the patient who has been treated with an IMP as part of a clinical trial, even though there may not be a causal relationship between the two. Therefore, an AE can be any unfavorable and/or unintended sign (e.g., an abnormal laboratory finding), symptom, or disease temporally associated with the use of an IMP, regardless of whether it is considered to be related to the investigational product or not. Abnormal test results should only be reported as AEs if they meet any of the following criteria, are associated with concomitant symptoms, and cannot be defined in general diagnostic terms. This includes abnormal symptoms and test results, or symptoms that call for additional diagnostic testing, pharmacologic intervention or surgery, a change in study drug dose or withdrawal from the study, those requiring additional concomitant drug treatment, or those that are considered an AE by the investigator or Sponsor.

The causal relationship between an AE and the IMP will be defined as follows:

Unrelated: The time relationship between the AE and the administration of the IMP makes a causal relationship between the two highly unlikely, or the patient's clinical status or the study procedures/conditions sufficiently explain the cause of the AE.

Related: The time relationship between the AE and the administration of the IMP makes a causal relationship between the two very likely, and the patient's clinical status or the study procedures/conditions do not sufficiently explain the cause of the AE.

The investigator will assess each AE to determine whether or not there exists a reasonable possibility that the AE is related to radium-223.

Toxicities will be reported using the descriptions and grade scales provided by the NCI-CTCAE version 4.0. A copy of the NCI-CTCAE criteria version 4.0 can be downloaded from the CTEP website (http://evs.nci.nih.gov/ftp1/CTCAE/CTCAE_4.03_2010-06-4_QuickReference_5x7.pdf).

When reported, the severity of an adverse event will be classified as one of the following:

- Mild - easily tolerated AE: It does not interfere with daily activities. CTCAE grade 1.
- Moderate: It causes some disruption of daily activities, may require intervention or treatment. CTCAE grade 2
- Severe: Considerable disruption of daily activities, need for hospitalization and/or surgical intervention or treatment. CTCAE grade 3 or 4.
- Fatal: Death. CTCAE grade 5
- Not applicable: Abnormalities in laboratory tests that are clinically significant and asymptomatic, or abnormal assessments not covered by the CTCAE scale, even though they are considered an AE.

A mild, moderate, or severe AE may or may not be serious. These terms are used for describing the severity of a specific event. Nevertheless, the medical significance of a severe event may be considered relatively minor (such as a severe headache) and may not be necessarily serious. For example, nausea lasting several hours may be considered severe, but may not be clinically serious. A fever of 39 °C which is not considered severe, may become serious if it results in a one-day hospital stay. Seriousness, rather than severity, serves as a guide for determining whether the event should be reported to authorities.

Adverse reactions to medicines: Any harmful and unexpected responses to an IMP (i.e. when there is at least reasonable possibility that there is a causal relationship between the IMP and the AE) that are related to any dose should be considered an adverse reaction to the medicine. In the case of marketed drugs, an adverse reaction to medicine is defined as a drug response that is harmful and unexpected and is produced at the dose that is normally administered to human subjects for prophylaxis, diagnosis or treatment of diseases, or to alter physiological functions.

An unexpected adverse reaction to a medicine is defined as an adverse reaction whose nature or severity is not consistent with the information on the product.

SAEs: By definition, a SAE is defined as any event that:

- Results in death.
- Is life-threatening.
- Requires hospitalization or prolongs existing hospitalization.
- Results in persistent or significant disability/incapacity (incapacity is defined as a significant disruption in a person's ability to perform normal life activities).
- Constitutes a congenital anomaly/birth defect.

Definition of life-threatening: An AE is life-threatening if the patient was at immediate risk of death due to the event; i.e. not including a reaction that could have caused death if it had been more serious. For example, a drug-induced hepatitis that resolved without signs of liver failure will not be considered life-threatening, even though drug-induced hepatitis can be fatal.

Definition of hospitalization: AEs that require hospitalization are considered serious. In general, hospitalization is considered as such when the patient has stayed (usually overnight) at a hospital or emergency room for observation or treatment that could not have been performed in a doctor's office or outpatient site. If there is some doubt as to whether the hospital stay can be considered "hospitalization" or whether it was necessary or not, the AE should be considered serious.

Hospitalization for scheduled surgery or standard clinical procedures which are not the result of an AE will not be considered an AE. If an incident arises during the procedure that is considered harmful, this should be reported as an AE and should be designated "serious" or "not serious" as per the standard criteria.

Definition of an event that is clinically or medically significant: Significant medical events that do not have a fatal outcome, regardless of whether they are life-threatening or require hospitalization, may be considered SAEs when, according to the appropriate medical opinion they put the patient's life at risk and may require medical or surgical intervention to prevent any of the outcomes listed in this definition. Examples of such medical events include allergic bronchospasm which requires intensive treatment in an emergency room or at home; blood dyscrasias; convulsions that do not result in hospitalization; or development of drug dependency or drug abuse. Clinically/medically significant events must be reported as SAEs.

For this clinical study and, according to this protocol, SAEs and hospitalizations related solely and unequivocally to the progression of the established tumor disease will not be treated as SAEs with regards to reporting obligations.

If the investigator becomes aware of a SAE at any time after the end of administration of study treatment and believes that it is possibly related to the study treatment (serious adverse reactions), he/she should notify the Sponsor.

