The Sponsor will compare the severity of each event and its cumulative frequency as reported in the study with the severity and frequency reported in the pertinent source document.

Reporting requirements are also based on the investigator's assessment of causality and seriousness, which may be updated by the Sponsor as needed.

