#### **8.4.3 *Adverse Events***

All AEs will be recorded on the eCRF "Adverse Events" page and will be coded using the current version of MedDRA® to give a system organ class (SOC) and preferred term (PT) for each event. All adverse event safety data will be updated to the version of MedDRA that is current at the time of the database lock and statistical analyses. Adverse events will be coded with grades defined according to CTCAE V4.0 criteria.

Treatment-emergent AEs (i.e. those events occurred after the first study medication administration and were not present at baseline or worsened in severity following the start of treatment) will be tabulated. The TEAE will be tabulated according to intensity and causality. If intensity of an AE or causality of an AE to the study medication is missing, a worst-case scenario will prevail (severe in intensity or probably related will be assumed). In the summary tables the number of subjects with events and the number of events will be presented.

The onset date of an AE will be compared to the date of first dose of study drug to determine whether or not the AE is treatment-emergent. Adverse events with an onset date on or after the date of first dose of study drug will be classified as treatment-emergent.

All deaths and SAEs, regardless of cause, from treatment up to three months after study discontinuation will be assessed. Non-fatal AEs occurring after treatment start regardless of cause, up to three months after study discontinuation or until start of new anti-cancer treatment, whichever is first will be assessed. SAEs and hospitalizations related solely and unequivocally to the progression of the established tumor disease will not be treated as SAEs as per protocol. Events that are continuations of baseline abnormalities are considered treatment emergent adverse events only if there is an increase in grade over baseline, or if there is an increase following a decrease during the study.

Treatment emergent adverse events with cause possibly related to treatment as judged by the investigator will be considered related to treatment. Events that are continuation of baseline abnormalities will not be considered treatment related unless there is an increase in grade, or if there is an increase following a decrease, and the increase is judged by the investigator to be due to treatment.

The following summaries will be provided:

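### Protocol 7.1 defines Related and Unrelated so that some adverse events fit neither, and its threshold conflicts with the reasonable-possibility test in the same section and with the SAP's causality levels

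*Protocol*

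**What the plan says.** Protocol 7.1 (Definitions of AEs) sets out two causality categories. An AE is Related when its timing relative to dosing "makes a causal relationship between the two very likely"; a second condition is that neither clinical status nor study procedures give a sufficient explanation. It is Unrelated when the timing "makes a causal relationship between the two highly unlikely, or the patient's clinical status or the study procedures/conditions sufficiently explain the cause". The connectives matter: both conditions must hold for Related, while either one is enough for Unrelated.

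The same section then uses other tests:

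- Directly after the two definitions, the investigator is to determine "whether or not there exists a reasonable possibility that the AE is related to radium-223".
- The definition of an adverse reaction applies "when there is at least reasonable possibility that there is a causal relationship between the IMP and the AE".
- For an SAE that comes to light after study treatment has ended, the instruction is that an investigator who "believes that it is possibly related to the study treatment (serious adverse reactions), he/she should notify the Sponsor".

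SAP 8.4.3 (Adverse Events) adds its own rule: "Treatment emergent adverse events with cause possibly related to treatment as judged by the investigator will be considered related to treatment". It also handles missing causality by a worst-case assumption, which it names as a probable relationship.

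Causality is used in three places. The opening of protocol section 7 limits the 7-day and 15-day reports to events related to the study drug, and protocol 7.2 says "Reporting requirements are also based on the investigator's assessment of causality and seriousness", while letting the sponsor update that assessment. The late-SAE instruction above turns on it. SAP 8.4.3 plans a separate summary of treatment-related TEAEs by SOC and PT.

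**The concern.** A causality scale has to give every event one answer, and the same answer wherever it is used. This one does neither. An investigator who follows the category definitions and one who follows the sentence after them can classify the same event differently, and both would be complying with section 7.1. The SAP then refers to levels that the protocol never defines.

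The trial is exposed to this because drug and disease explanations overlap. Protocol 6.11 lists nausea and hematological complications among the features of progression, then notes that treatment can change hematology parameters. Protocol 1.2 lists nausea and several cytopenias among the common findings on radium-223. Safety is a secondary objective and the design is single-arm (protocol 2.2 and 3.1), so there is no control rate to show whether attribution has gone wrong.

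**Working it through.** The plan states no figure on this point, so the check is logical. Treat the two definitions as conditions on two inputs: timing (causation highly unlikely, intermediate, or very likely) and whether clinical status or procedures sufficiently explain the event (yes or no). That gives 3 × 2 = 6 combinations.

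| Timing | Sufficient alternative explanation? | Category under the 7.1 definitions | Could a reasonable-possibility test say Related? |
|---|---|---|---|
| Highly unlikely | Yes | Unrelated | No |
| Highly unlikely | No | Unrelated | No |
| Intermediate | Yes | Unrelated | Yes, on judgement |
| Intermediate | No | None | Yes |
| Very likely | Yes | Unrelated | Yes, on judgement |
| Very likely | No | Related | Yes |

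Unrelated covers 2 + 1 + 1 = 4 combinations, Related covers 1, and 6 − 4 − 1 = 1 has no category. The two tests agree in three rows (both highly-unlikely rows and the last). They can differ in the other three: one row is unclassified, and two are forced to Unrelated whatever the investigator thinks of the possibility. These are counts of logical cases and not proportions of events, because the documents do not say how often each arises.

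Following the conflict through the documents:

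1. **Within protocol 7.1.** An event with very likely timing and a sufficient disease explanation is Unrelated by definition. If the investigator still sees a reasonable possibility of a drug cause, it is also an adverse reaction under the same section. Both cannot stand.
2. **Late SAEs.** These are notified if possibly related. A possible relationship is not an answer on the two-category scale, and an investigator working from that scale could answer Unrelated and not notify.
3. **Protocol to SAP.** The SAP rule needs a possible level, which the protocol's scale lacks. Its imputation assigns a probable level, which is also absent.
4. **Effect on the related-TEAE table.** An event whose causality is left blank is counted as related. The same event, assessed under the definitions, could be Unrelated. The table can therefore mix thresholds.

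**The case against.** The strongest reply is that causality is only a label here and no event is lost. Protocol 7.2 has all AEs entered in the CRF, and all SAEs and AESIs sent to the sponsor within 24 hours whatever the causality. The synopsis says that AEs judged unrelated are reported too. SAP 8.4.3 tabulates all TEAEs by SOC, PT and intensity, and SAP 8.4.4 tabulates hematology values with changes from baseline. This stands, with one limit: AE collection ends three months after progression, and an SAE arising later, other than a followed skeletal event or a death, reaches the sponsor only through the causality-dependent instruction.

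The direction of any error can also be disputed. The reasonable-possibility sentence sits directly after the definitions, the SAP leans towards related, and the sponsor may update causality. This too stands in part: it makes understatement a risk and not a certainty. It does not remove the inconsistency, since sites may choose different tests and no criterion is given for the sponsor's update.

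A reader might infer that cytopenias and nausea will routinely be called Unrelated because bone metastases could also explain them. The definition asks whether clinical status sufficiently explains the event, which is a higher bar. Enrolled patients are asymptomatic, have ECOG 0–1 and face hematology exclusions at screening (protocol 4.2 and 4.3), so disease is not automatically a sufficient explanation.

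A reader might also try to size the effect from the ALSYMPCA rates in protocol 1.2, for example 20% grade 3–4 lymphocytopenia, or 52 × 0.20 = 10.4 patients, and contrast none with all of them being called related. Those are rates of laboratory abnormality whatever the cause, protocol 7.1 restricts which abnormal results become AEs, and the contrast only pairs two assumed extremes.

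**Conclusion.** The causality definitions leave a gap and conflict with other tests in protocol 7.1 and SAP 8.4.3. That follows from the wording alone. The consequence is a risk that the related-TEAE table, expedited reporting and late-SAE notification are inconsistent between investigators or understated.

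It would go too far to say that drug reactions are under-reported. Capture within the collection window does not depend on causality, and the documents contain no attribution data. The size cannot be estimated. Expected cytopenias would mainly affect the tables: the 7-day route covers unexpected events, and expectedness is judged against the SmPC, so they are poor examples of a missed expedited report.

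One thing is unknown. SAP 4.1 cites eCRF Version 4.0, but its causality options are not shown. If it offers possible and probable, the SAP matches the eCRF but not the protocol; if it is binary, the SAP matches neither. A conflict remains either way. The primary endpoint, sample size and analysis sets are unaffected.

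**What to change.** Reconcile the passages in protocol 7.1 and SAP 8.4.3 to one binary threshold, using a concept that section 7.1 already contains:

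- **Related:** there is at least a reasonable possibility that the IMP caused the AE.
- **Unrelated:** there is no reasonable possibility that it did.
- An alternative explanation may inform that judgement but should not by itself force Unrelated.
- The late-SAE instruction should use the same threshold.
- In SAP 8.4.3, use the same two levels and impute missing causality as related. Check the eCRF options first; if they have more than two levels, state how each maps to the binary scale.

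The cost is protocol and SAP wording plus CRF completion guidance. The downside is a somewhat higher related-event count and possibly a few more expedited reports.

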Radium-223 (Xofigo[®]) is indicated for the treatment of patients with mCRPC with symptomatic bone metastases and no known visceral metastatic disease. In the pivotal phase III clinical trial (the ALSYMPCA study), a total of 921 subjects with mCRPC with bone metastases were randomly assigned, in a 2:1 ratio, to receive six injections of radium-223 (at a dose of 50 kBq per kilogram of body weight intravenously) or matching placebo; one injection was administered every four weeks[16]. Prior to randomization, 58% and 57% of patients had received docetaxel in the radium-223 and placebo arms, respectively. The median duration of treatment was 20 weeks (six cycles) for radium-223 and 18 weeks (five cycles) for placebo. Radium-223, as compared with placebo, significantly improved OS (median, 14.0 vs. 11.2 months; HR, 0.70; 95% CI, 0.55 to 0.88; P=0.002). The updated analysis involving 921 patients confirmed the radium-223 survival benefit (median, 14.9 vs. 11.3 months; HR, 0.70; 95% CI, 0.58 to 0.83; P<0.001). Assessments of all main secondary efficacy endpoints also showed a benefit of radium-223 as compared with placebo. The most common AEs ($\geq 10\%$) in patients receiving radium-223 were nausea (2% grade 3-4), diarrhea (2% grade 3-4), vomiting (2% grade 3-4), and peripheral edema (2% grade 3-4). The most common hematologic laboratory abnormalities in radium-223-treated patients ($\geq 10\%$) were anemia (6% grade 3-4), lymphocytopenia (20% grade 3-4), leukopenia (3% grade 3-4), thrombocytopenia (3% grade 3-4), and neutropenia (2% grade 3-4). Treatment discontinuations due to AEs occurred in 17% of patients who received radium-223 and 21% of patients who received placebo.

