2.2. Secondary objectives

- Safety profile.
- To determine the association between AR-V7 status (positive vs. negative) and PFS.
- To establish the relationship between CTCs number with radium-223 efficacy.

Secondary endpoints:

Safety

AEs will be evaluated using the Common Terminology Criteria for Adverse Events(CTCAE) of the US National Cancer Institute (NCI) version 4.0[20]. Grade 3 or 4 AEs and serious adverse events (SAEs) will be assessed to determine the safety and tolerability of the various combinations of drugs.

Efficacy

- Radiographic progression-free survival (rPFS) depending on AR-V7 status.
- Overall survival (OS).
- Time to first symptomatic skeletal event (SSE).
- Time to PSA progression according to the ALSYMPCA study criteria.
- Determination percentage of PSA progresion.
- Alkaline phosphatase level response (AF), normalization of alkaline phosphatase level, according to the ALSYMPCA study criteria.

Molecular aspects

- Assessment of AR-V7 mutation evolution during the study treatment.
- Determination changes in CTCs number during the study treatment.

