#### **Secondary endpoints:**

##### Safety:

AEs will be evaluated using the Common Terminology Criteria for Adverse Events (CTCAE) of the US National Cancer Institute (NCI) version 4.0. AEs and serious adverse events (SAEs) will be assessed to determine the safety and tolerability of the various combinations of drugs.

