#### **8.4.4 Clinical Laboratory Parameters**

All hematology, coagulation and biochemistry parameters (including PSA and testosterone) will be presented by descriptive statistics in a tabulated summary by time point of assessment for full analysis set together with the respective changes from baseline. In addition, a frequency table for clinically significant values will be presented by time point of assessment.

A by-subject listing for these parameters will be also provided. These listings will be presented for full analysis set and time point and will include: site, subject identifier, laboratory parameter, parameter values (in SI units), SI unit, normal range and a flag with respect to normal range (below, within and above normal range).

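### Protocol 7.1 puts clinically significant asymptomatic laboratory abnormalities outside the severity scale, against the CTCAE grading required elsewhere, and SAP 8.4.4 plans no laboratory table by CTCAE grade

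*Protocol*

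**What the plan says.** **Endpoint.** Protocol 2.2: "Grade 3 or 4 AEs and serious adverse events (SAEs) will be assessed to determine the safety and tolerability". The corresponding SAP text (5.2, Safety) omits the grade restriction: "AEs and serious adverse events (SAEs) will be assessed to determine the safety and tolerability of the various combinations of drugs".

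**Reporting.** Protocol 7.1 counts an abnormal laboratory finding among possible adverse events and then limits when one is reported: "Abnormal test results should only be reported as AEs if they meet any of the following criteria, are associated with concomitant symptoms". The same passage goes on to list circumstances that need no symptoms, such as further testing, intervention or a change in study drug, and ends with "those requiring additional concomitant drug treatment, or those that are considered an AE by the investigator or Sponsor".

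**Grading.** Protocol 7.1: "Toxicities will be reported using the descriptions and grade scales provided by the NCI-CTCAE version 4.0". Its severity list ties mild to grade 1, moderate to grade 2, severe to grades 3 and 4, and fatal to grade 5. It then adds a last category: "Not applicable: Abnormalities in laboratory tests that are clinically significant and asymptomatic, or abnormal assessments not covered by the CTCAE scale". That sentence ends by accepting that such findings are adverse events. Footnote 7 of Protocol Appendix 1 requires all adverse events to be recorded with a CTCAE 4.0 grade, and SAP 8.4.3 codes adverse events with CTCAE grades.

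**Laboratory tables.** SAP 8.4.4 plans descriptive statistics and changes from baseline by time point, a listing that flags each value as below, within or above the normal range, and "a frequency table for clinically significant values will be presented by time point of assessment". It mentions no CTCAE grade.

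**The concern.** The *Not applicable* category has two limbs. The second, for findings CTCAE does not cover, is unobjectionable. The first is defined by the absence of symptoms, so it also takes in blood counts that CTCAE does grade. An investigator who reports a symptomless grade 3 or 4 count as an adverse event, and then follows the severity list literally, gives it a label outside the category that corresponds to grades 3 and 4. An investigator who follows Appendix 1 records the grade. Both are following the protocol.

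At stake is whether the grade 3-4 count measures the same thing at every site. Haematological change is a prominent expected effect in the protocol's own background (section 1.2), and it is the kind of effect that this wording touches. If the adverse event tables are the only place where grades appear, a reader of the report cannot tell a low rate from a labelling habit.

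**Working it through.** The plan states no figure to reproduce; this is a comparison of rules. Take a lymphocyte count in the CTCAE grade 3 range on a day 1 blood test, with no symptoms, no treatment and no dosing delay, and follow it through the documents.

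1. **Is it an adverse event?** Under Protocol 7.1 the answer depends on how the sentence is read. It asks for any one of several criteria but joins them with a conjunction, as if all were needed. Read as alternatives, investigator or Sponsor judgement is enough. Read cumulatively, the lack of symptoms keeps it out.

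2. **If reported, does it carry a grade?** The rules disagree:

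| Source | Treatment of the event |
|---|---|
| Protocol 7.1, toxicity sentence | CTCAE 4.0 grade |
| Protocol 7.1, severity list | *Not applicable* if clinically significant and asymptomatic |
| Protocol Appendix 1, footnote 7 | CTCAE 4.0 grade for every adverse event |
| SAP 8.4.3 | CTCAE 4.0 grade |

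3. **Does another rule force a grade?** Protocol 6.11 uses grade 3 or 4 neutropenia, thrombocytopenia and anemia in its delay rules, so sites must grade those three counts. It names neither lymphocytopenia nor leukopenia.

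4. **Does the SAP restore a lost grade?** Four provisions come close; none is stated to do so.
   - 8.4.3 treats missing intensity as severe, but an entry of *Not applicable* is not missing.
   - 8.4.3 also tabulates maximal toxicity grade by type, without saying that laboratory values feed that table.
   - 8.2 allows shift tables for categorical data where appropriate, but no laboratory grade variable is defined.
   - 8.4.4 offers only the clinically significant count and the normal-range flag. Neither separates grade 1 from grade 4.

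**Scale, for orientation only.** Protocol 1.2 quotes grade 3-4 haematologic laboratory rates from the pivotal phase III trial. Applying them to this trial's 52 patients is an assumption, since the population differs. Expected patients = 52 × rate:

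- lymphocytopenia: 52 × 0.20 = 10.4
- anemia: 52 × 0.06 = 3.1
- leukopenia: 52 × 0.03 = 1.6
- thrombocytopenia: 52 × 0.03 = 1.6
- neutropenia: 52 × 0.02 = 1.0

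If a share m of true grade 3-4 lymphocytopenia cases is left ungraded, the graded rate is 20% × (1 − m). At m = 0 this is 20%, at m = 0.5 it is 10%, and at m = 1 it is 0%. Nothing in the documents narrows m, so the calculation shows which counts could be affected, not by how much.

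**The case against.** The strongest reply is that the documents do require grading. Appendix 1 footnote 7 covers all adverse events, SAP 8.4.3 repeats the requirement, and the deviation table in SAP 6.1 expects a listing of grade 3/4 events with no action taken. On this view *Not applicable* belongs to a separate verbal severity scale, and a site would still enter a grade. That is a fair reading, and it is why the defect is a conflict between rules rather than an absent rule. It does not remove the conflict, because the severity list in 7.1 is itself expressed in CTCAE grades.

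Three stronger readings are tempting and should not be drawn.

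- *That laboratory abnormalities are reported only when symptomatic.* Section 7.1 lists routes that need no symptoms, and its severity list accepts asymptomatic findings as adverse events. Non-reporting is one possible result of an inconsistent sentence, not the rule.
- *That marrow toxicity would go unseen.* Sites must grade neutropenia, thrombocytopenia and anemia to apply 6.11. Section 7.1 gives blood dyscrasias as an example of events that may be medically significant SAEs, although this rests on medical opinion and supplies no grade. SAP 8.4.4 lists values by subject and time point. The data are kept; what is missing is a graded summary.
- *That the undercount can be stated, for example 5% shown instead of a true 20%.* No source gives the asymptomatic share, and the 20% is a laboratory rate that section 1.2 lists separately from adverse events. The plan also does not propose a formal comparison with those rates.

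**Conclusion.** The concern holds as an unresolved conflict combined with a missing table. Protocol 7.1 contradicts its own toxicity sentence, Appendix 1 and SAP 8.4.3 on whether a symptomless laboratory adverse event carries a CTCAE grade, and it is unclear on when such an abnormality is reported. Because SAP 8.4.4 derives no grades, nothing planned corrects for differences in how sites resolve this.

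The grade 3-4 counts may therefore understate haematological toxicity and vary by site. Exposure is greatest for lymphocytopenia and leukopenia. The direction assumes that at least some sites apply the *Not applicable* wording literally; the amount cannot be estimated. The consequence is confined to a secondary, descriptive endpoint and does not touch the primary analysis. It still merits correction, because a stated rule can remove graded toxicity from a stated endpoint and the remedy uses data already collected.

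**What to change.** **Protocol 7.1 and Appendix 1, with SAP 8.4.3.** Reconcile the three. Limit *Not applicable* to assessments that CTCAE does not grade, and state that any adverse event CTCAE grades keeps its grade with or without symptoms. Rewrite the reporting sentence so that it is clear whether its criteria are alternatives.

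**SAP 8.4.4.** Derive CTCAE 4.0 grades from the haematology and biochemistry values already collected. Tabulate worst post-baseline grade and the shift from baseline to worst grade, and report grade 3-4 laboratory rates from that table alongside the adverse event tables.

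**Population.** Specify the safety set for this table. SAP section 6 assigns safety analyses to that set, whereas 8.4 and 8.4.4 name the full analysis set. The footnote to the deviation table in 6.1 removes patients with major deviations from the full analysis set, and that table classes day 1 laboratory tests done outside the 72-hour window as major.

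**Cost.** A few sentences and one additional programmed output, with no new assessments. Reported grade 3-4 rates may be higher than the adverse event tables alone would show.
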